7.5 Follow-up

7.5.1 Safety follow-up

For eligible patients, SAE and AE monitoring will continue until 125 days after the last administration of BI-1206 and or rituximab on study (whichever is later) or until the patient starts another anti-cancer therapy (see Section 9.6). Any drug-related AEs still ongoing after this period will be followed up monthly until resolution to baseline or stabilisation, unless the patient starts another anti-cancer therapy.

Should an Investigator become aware of any drug-related SAEs after this period (even if the patient has started another anti-cancer therapy) these must also be reported to the CDD within the expedited timelines in Section 9.7.

7.5.2 Efficacy and survival follow-up

All patients will be followed up for survival at one year (to be calculated from the date of their first BI-1206 treatment) and subsequently until the last patient has completed one year of follow-up from the date of their first BI-1206 treatment.

Contact will be made at routine follow-up appointments (approximately every 16 weeks) to assess survival status. Information on disease status will also be captured for any patients who have not shown progressive disease at the time of their off-study visit.

Survival (and if applicable, disease status) will be captured every approximately every 16 weeks from the off study visit, up to 1 year after the patient started study treatment and then every 6 months until the last patient has completed one year of follow-up from the date of their first BI-1206 treatment.

7.6 Schedule of events

Observation/Investigation	Screening		Induction Therapy								Week 5	Week 8	Maintenance Therapy (i)	Off-study visit	Survival Follow-up	
	Within weeks	4	Within 1 week	Week 1		Week 2		Week 3		Week 4		Day 29 (+3 days)	Day 50 (+1 week) Decision point: Patient to continue onto maintenance therapy or off study	Every 8 weeks (±2 wks)		Every 16 weeks up to one year, then every 6 months or at clinic visits.
				Day 1	Day 4	Day 8	Day 11	Day 15	Day 18	Day 22	Day 25					
Written informed consent	X															
Demographics & Medical history	X															
Adverse event evaluation	From date of informed consent		Continually review						X		X		X	X (k)		
Concomitant treatments	X	X		Continually review						X		X		X	X	
Confirmation of CD20+ disease (patients treated with rituximab) (a)	X															
CD32b expression in Part A/ CD32b+ disease in Part B	X (q)															
Disease assessment by CT	X										X		X (j)	X (j)		
Clinical disease assessment (if applicable)		X									X		X (j)	X (j)		
FDG-PET (Non-WM lymphoma patients)	X										X		(X (j))			
Serum Paraprotein (WM patients)	X										X		X	X		
Bone marrow aspirate (and trephine) (m)	X										X (if CR)		X (if CR (j))	X (if CR)		
Pregnancy test (b)		X														
Height, weight, BSA (c)		X											X (c)			
Physical examination (d)		X		X						X		X		X	X	
Hep B/ C/ HIV	X															
Temperature, blood pressure, pulse and SaO ₂ (p)		X	X		X		X		X		X		X	X	X	
WHO performance status		X	X	(X) ^l	X	(X) ^l	X	(X) ^l	X	(X) ^l	X		X	X	X	

CONFIDENTIAL

Observation/Investigation	Screening		Induction Therapy								Week 5	Week 8	Maintenance Therapy (i)	Off-study visit	Survival Follow-up	
	Within weeks	4	Within 1 week	Week 1		Week 2		Week 3		Week 4		Day 29 (+3 days)	Day 50 (+1 week) Decision point: Patient to continue onto maintenance therapy or off study	Every 8 weeks (±2 wks)		Every 16 weeks up to one year, then every 6 months or at clinic visits.
				Day 1	Day 4	Day 8	Day 11	Day 15	Day 18	Day 22	Day 25					
Haematology and biochemistry (e) including B and T Lymphocytes		X		X	X	X	(X) ^l	X	(X) ^l	X	(X) ^l		X	X	X	
Urine sample for urinalysis		X		X	X	X	(X) ^l	X	(X) ^l	X	(X) ^l		X	X	X	
Serum Immunoglobulins (IgA, IgG, IgM)	X												X	(X, WM pts IgM every 16 wks)	X	
Beta-2-microglobulin	X												X		X	
Coagulation		X														
Autoimmune assessment		X											X	X	X	X
Eye examination (f)	X												(X)	X	(X)	X
Electrocardiogram (ECG) (g)	X												(X)	(X)	(X)	(X)
Premedication (h)			X		X		X		X		X			X (i)		
BI-1206/ rituximab administration (h)			X		X		X		X		X			X (i)		
PK sampling (see Section 8)			X	X	X	X	X	X	X	X	X			X		
PD sampling (see Section 8)		X	X	X (o)	X	X (o)	X	X (o)	X	X (o)	X		X	X	X	
Follow-up contact for survival/progression (n)																X

(a) In patients that are refractory to rituximab, i.e either progressing whilst on rituximab based therapy (induction or maintenance) or progressing within 6 months of their last dose of rituximab, a biopsy should be performed prior to study entry to ensure that there is continued expression of CD20.

(b) Pregnancy test: For female patients of child bearing potential within 2 weeks before receiving BI-1206.

(c) Weight measured during screening should be used for BSA calculation for induction therapy. For maintenance treatment, weight should be measured prior to each dose and BSA recalculated if the patient's weight has changed by more than 10% from the weight used for the current BSA (i.e. weight at 1st maintenance will be compared to weight measured at screening), there is no need to re-measure height.

(d) Complete physical examination to be performed pre-study then all subsequent examinations can be symptom-directed or as clinically indicated.

CONFIDENTIAL

(e) Clinical laboratory assessments should be performed prior to each BI-1206 infusion (and before each rituximab administration if given on a different day to BI-1206). Laboratory tests can be performed up to 24 h prior to each infusion but results must be available and reviewed by the investigator before BI-1206/rituximab is given. In the event of a Grade 4 neutropenia or Grade 4 thrombocytopenia a full blood count must be performed at least on Day 5 (Day 10 for neutropenia) after the onset of the event to determine if a dose limiting toxicity has occurred. Monitoring must continue until resolution to Grade 3 or less. At screening, GFR measurement may be required if there is a concern regarding the calculated creatinine clearance measurement).

If split dosing is implemented, laboratory tests will be relative to the first infusion administered each week then as clinically indicated on the second day.

(f) Eye exam, performed by ophthalmologist to be performed at screening, week 8 and off-study and otherwise as clinically indicated.

(g) ECG to be performed pre-study and otherwise as clinically indicated.

(h) For patients recruited to Part A & B, Arm 2, rituximab to be given on Day 2 post BI-1206 at Week 1. If infusion time permits, then subsequent doses of rituximab will be given on the same day as BI-1206. Maintenance treatment (from Week 8) will only be given if a patient is deemed eligible to continue on to maintenance treatment following Week 8 assessments.

If split dosing is implemented, laboratory tests will be relative to the first infusion administered each week then as clinically indicated on the second day.

(i) Maintenance therapy will only be given to those patients who demonstrate stable or responding disease and will start after the Week 8 scan results following induction therapy confirming patient is eligible for maintenance treatment. Patients will receive the same dose of BI-1206 (and rituximab if received) as in their induction therapy from week 8 onwards (i.e. Week 9 or 10) and every 8 weeks (\pm 2 weeks) from the first maintenance dose, for up to one year from first induction dose.

(j) A CT scan to assess the patient's tumour burden to be performed at Week 8 (prior to commencing maintenance therapy) and then every 16 weeks (\pm 2 weeks) during maintenance therapy and at off-study. Patients with Waldenstrom's macroglobulinaemia will also have serum paraprotein samples taken at these time points. If a complete response is noted, a bone marrow biopsy may be performed and in a lymphoma patient with PET-avid disease a FDG-PET scan will also be performed. A scan is only required at Off-study if no appropriate disease assessment has been performed recently (at week 8 or as required on maintenance).

(k) Monthly follow-up required ONLY for those AEs and SAEs considered drug-related (highly probable, probable or possible) and present at off-study. Monthly follow-up for AEs to continue until resolution, return to baseline, stabilisation or patient starts another anti-cancer treatment.

(l) Day 11, 18, 25 assessments performed for patients in Cohort 1, Arm 1 only.

(m) Bone marrow aspirate samples are used for pharmacodynamic analysis, trephine samples are to be taken where required for disease assessment, if a sample is taken as part of routine care within 8 weeks prior to starting on the study a repeat baseline sample is not required. After baseline, a bone marrow sample is only required for disease assessment to confirm at complete response.

(n) Follow-up will continue until the last patient has completed one year of follow-up from the date of their first BI-1206 treatment.

(o) Samples may also be taken on Day 2 and/or Day 4 after each weekly dose during weeks 1-4, emerging data will be reviewed at dose review meetings and a decision will be made for the following cohort as to whether or not these samples are required. Schedule may also differ between arms due to logistical reasons, refer to Study Laboratory Manual for details

(p) Oxygen saturation levels (SaO₂) to be performed pre-study, prior to each dose during Week 1- 4 (induction therapy) and otherwise as clinically indicated

(q) Part A: CD32b expression assessed centrally by blood, bone marrow sample and/or lymph node sample and to be sent during screening assessments. For Part B: CD32b positivity to be confirmed during pre-screening.

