BI-1206 and rituximab will each be administered once weekly for four weeks via separate IV infusions. Based on the proposed mechanism of action of BI-1206 binding to the CD32b receptor and blocking its ability to internalise rituximab, BI-1206 will be administered prior to rituximab. The timeframe within which the two infusions can be given (i.e. on the same day or on subsequent days) will be determined by the length of each infusion. At Week 1 both infusions will be administered over a longer period of time as a precautionary measure and so the BI-1206 dose will be given on Day 1 and the rituximab dose on Day 2. In subsequent weeks, if patients have not experienced a significant infusion reaction at Week 1 then the BI-1206 and rituximab infusions can be given at a faster rate. Therefore, from Week 2 onwards, if the infusion times allow, the doses of BI-1206 and rituximab may be given on the same day. BI-1206 will be given prior to rituximab on all occasions. If infusion times are not compatible with same-day dosing, administration of BI-1206 and rituximab on subsequent days will continue. These cohorts will include a minimum of one patient as described in Section 5.5.

Patients who show clinical benefit at eight weeks (as defined in Section 10.2) will move to a maintenance phase of treatment (refer to Section 5.2.5).

Figure 3: Combination dosing schedule during induction therapy

	Week 1				Week 2				Week 3				Week 4			
	D1	D2	D3	D4	D8	D9	D10	D11	D15	D16	D17	D18	D22	D23	D24	D25
BI-1206	X				X				X				X			
Rituximab			X		X ¹				X ¹				X ¹			

¹ Rituximab may be given on Day 1 following BI-1206 from Week 2 onwards if no significant infusion reaction has been observed at Week 1 and if infusion times allow this.

Otherwise it will be given on Day 2 as in Week 1.

5.2.3 Dosing schedule/treatment schedule in BI-1206 single agent expansion phase (Part B, Arm 1)

BI-1206 will be administered once weekly for four weeks via IV infusion at the RP2D as defined by Part A, Arm 1 this will be classified as induction therapy; refer to Section 5.7. Patients with clinical benefit (as defined in Section 10.2) at eight weeks will move to a maintenance phase of treatment as described in Section 5.2.5.

5.2.4 Dosing schedule/treatment schedule in BI-1206/rituximab combination expansion phase (Part B, Arm 2)

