BI-1206 and rituximab will each be administered once weekly for four weeks via separate IV infusions. BI-1206 will be administered at the RP2D as defined in Part A, Arm 2 and rituximab at the fixed dose of 375 mg/m²; this will be classified as induction therapy, refer to Section 5.8. Patients with clinical benefit (as defined in Section 10.2) at eight weeks will move to a maintenance phase of treatment as described in Section 5.2.5.

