8.3.1.3 Pharmacokinetic sampling, Part A & B, Arm 2 (BI-1206 plus rituximab)

For patients receiving **combination therapy with BI-1206 and rituximab in the Part B Arm 2 expansion**: a 6 mL blood sample will be taken pre- BI-1206 infusion, at the end of the BI-1206 infusion (+5 mins), 4 hours after the end of the BI-1206 infusion (\pm 15 mins), at 24 hours after the BI-1206 infusion (before the rituximab infusion) and at 72 hours after the BI-1206 infusion at Week 1. Samples will also be taken pre- BI-1206 infusion at Weeks 2 and 3. At Week 4, samples will be taken prior to the BI-1206 infusion, at the end of the BI-1206 infusion, 4 hours after the BI-1206 infusion (or if rituximab is given on the same day, at the end of rituximab infusion), at 24 hours after the BI-1206 infusion (before the rituximab infusion) and at 72 hours after the BI-1206 infusion. During the maintenance period, a sample will be taken prior to each BI-1206 infusion. The approximate volume of blood withdrawn from each patient in the Part B expansion be 72 mL during the induction period with an additional 36 mL withdrawn over the subsequent maintenance treatment period (Table 5).

Table 5: Parts A & B Arm 2, combination PK sampling schedule

Time	Induction				Maintenance
	Week 1	Week 2	Week 3	Week 4	
Pre	X	X	X	X	X
EOI (BI-1206)	X			X	
+ 4hrs (BI-1206)	X			X ^	
+ 24hrs (BI-1206)	X			X	
+72hrs (BI-1206)	X			X	
Total (mL)	72				(up to 36)

[^] If rituximab is given on Day 1, this sample will be at the end of rituximab infusion instead

For split dosing administration of BI-1206 plus rituximab:

- Up to 18 PK time points may be taken during the induction period (8 weeks) with an additional 6 PK timepoints thereafter (to include pre-infusion sampling during the maintenance phase). This will be approximately 108 mLs taken over the first eight weeks with approximately 36mLs taken post the induction phase, throughout the maintenance phase.
- If split dosing is implemented, the blood volume requested may increase from 72 mL to 108 mL, over the first eight weeks.
- Please refer to the study laboratory manual for handling, adjusted sample times, sample volume per time point, storage and shipment of samples.

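### For Part A, Arm 2, schedule note (h) allows same-day rituximab from Week 2 on infusion time alone, whereas the Figure 3 footnote also requires that Week 1 passed without a significant infusion reaction

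*Combined protocol and SAP*

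**What the plan says.** Three places in the protocol deal with the day on which rituximab is given in the combination arms.

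- **Section 5.2.2, body text (Part A, Arm 2).** The spacing of the two infusions depends on how long each one takes. At Week 1 they are on separate days. After that, "if patients have not experienced a significant infusion reaction at Week 1 then the BI-1206 and rituximab infusions can be given at a faster rate". The next sentence draws the consequence: "Therefore, from Week 2 onwards, if the infusion times allow, the doses of BI-1206 and rituximab may be given on the same day". If the times do not fit, dosing on consecutive days continues.
- **Section 5.2.2, Figure 3, footnote 1.** Rituximab may follow BI-1206 on Day 1 from Week 2 "if no significant infusion reaction has been observed at Week 1 and if infusion times allow this". The footnote then sets a default: "Otherwise it will be given on Day 2 as in Week 1".
- **Section 7.6, note (h).** This note is attached to the premedication and administration rows of the schedule. It opens "For patients recruited to Part A & B, Arm 2, rituximab to be given on Day 2 post BI-1206 at Week 1" and continues "If infusion time permits, then subsequent doses of rituximab will be given on the same day as BI-1206". It mentions no reaction and does not refer back to Section 5.2.2.

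The pharmacokinetic sampling text also treats same-day dosing as an option: "If rituximab is given on Day 1, this sample will be at the end of rituximab infusion instead" (Section 8.3.1.3, Table 5 footnote). For Part B, Arm 2, Section 5.2.4 gives the doses ("BI-1206 will be administered at the RP2D as defined in Part A, Arm 2 and rituximab at the fixed dose of 375" mg/m²) and the weekly schedule, but no condition for same-day dosing.

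**The concern.** Note (h) drops one of the footnote's two conditions and turns a permission into an instruction. The condition it drops is the safety one. The footnote keeps the two antibodies on separate days for a patient who reacted significantly at Week 1, whether or not the infusions would fit into one day. Note (h) puts that same patient on same-day dosing whenever they fit.

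What is at stake is a precaution that the sponsor wrote for a first-in-human combination. Section 2.2.6 reports infusion-related reactions in more than 50% of rituximab patients, mostly at the first infusion. Section 2.2.8 expects such reactions with BI-1206 as well, and warns that the combination could make rituximab's effects worse. Sites are likely to book treatment from the schedule of events, which is where the condition is missing.

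**Working it through.** The plan gives no figure to reproduce here. The check is a comparison of two rules, followed by an illustration of whether the time test could stand in for the reaction test.

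**1. The two rules, for Part A, Arm 2, Weeks 2 to 4**

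| Week 1 significant reaction | Infusions fit in one day | Figure 3 footnote | Note (h) |
|---|---|---|---|
| No | Yes | same day permitted | same day instructed |
| No | No | Day 2 | same day not called for |
| Yes | No | Day 2 | same day not called for |
| **Yes** | **Yes** | **Day 2** | **same day instructed** |

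The rules give opposite instructions only in the last row. The first row differs in force (may against will), not in direction.

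**2. Does other text restore the condition?**

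- Section 5.9.2 ends treatment after severe, life-threatening reactions. For other Week 1 reactions it offers split dosing of BI-1206, with rate and split agreed with the Sponsor and CI.
- Sections 6.2.5.6 and 6.2.11.2 call for discussion with the Sponsor and CI if an infusion is interrupted for an adverse event and the full dose is not given.
- Sections 7.2 and 8.3.1.3 only describe monitoring and sampling where both antibodies are given on one day.

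None of these returns rituximab to Day 2 because of a Week 1 reaction.

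**3. Can a patient kept at the slower rates still pass the time test?** This part is illustrative only.

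*Inputs from the protocol:* rituximab 375 mg/m². First-infusion rituximab steps (6.2.11) start at 50 mg/h and rise by 50 mg/h every 30 minutes to 400 mg/h. BI-1206 above 50 mg (6.2.5.4) starts at 50 mg/h, with increases at 30-minute intervals to a maximum of 400 mg/h. Premedication is at least 30 minutes before each infusion, and monitoring at least 30 minutes after each infusion from Week 2 (5.9.2).

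*Assumptions:* BI-1206 rises in the same steps as rituximab (its actual steps are in the pharmacy guidelines, which are not part of the documents). BSA is 1.6 to 2.2 m². There is no interruption. The working day is 8 h; the protocol sets no limit.

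*Cumulative dose* at 0.5, 1.0, 1.5, 2.0, 2.5, 3.0 and 3.5 h: 25, 75, 150, 250, 375, 525 and 700 mg, then 400 mg/h.

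*Infusion times*
- BI-1206 100 mg: 1.0 + 25/150 = 1.17 h
- BI-1206 200 mg: 1.5 + 50/200 = 1.75 h
- BI-1206 400 mg: 2.5 + 25/300 = 2.58 h
- BI-1206 800 mg: 3.5 + 100/400 = 3.75 h
- Rituximab 375 × 1.6 = 600 mg: 3.0 + 75/350 = 3.21 h
- Rituximab 375 × 2.2 = 825 mg: 3.5 + 125/400 = 3.81 h

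*Visit length* = BI-1206 time + rituximab time + 1.5 h (monitoring and second premedication overlap) to 2.0 h (no overlap):

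| BI-1206 dose | Visit length at first-infusion rates |
|---|---|
| 100 mg | 5.9 to 7.0 h |
| 200 mg | 6.5 to 7.6 h |
| 400 mg | 7.3 to 8.4 h |
| 800 mg | 8.5 to 9.6 h |

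With every rate halved, BI-1206 100 mg takes 1.75 h and rituximab 4.75 to 5.88 h, so the visit takes 1.75 + 4.75 + 1.5 = 8.0 h to 1.75 + 5.88 + 2.0 = 9.6 h.

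On these assumptions, a patient who reacted could pass the time test at 100 to 200 mg. A fit is not shown at 800 mg, and at half rate for both antibodies 100 mg reaches or exceeds the assumed day. Low doses are realistic: Section 5.1.1 lets Arm 2 start once Cohort 1, which escalates to 50 mg, is complete.

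**The case against.** The best defence is that note (h) condenses the body text of Section 5.2.2. There, infusion length is the main test and the reaction enters through it: without a significant reaction the rates can rise, and faster rates make one day feasible. The body text's own fallback to consecutive days mentions only time. On that reading the footnote is stricter than both the body text and note (h). This stands in part: the separate reaction test and the Day 2 default are explicit only in the footnote. It does not remove the conflict. The footnote joins two conditions with *and*, and slower infusions may still fit in a day.

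A second defence is that these patients are not unprotected. Premedication, stopping rules, optional split dosing, discussion of incomplete doses, and vital signs between same-day infusions all apply (Sections 5.9.2, 6.2.5.6, 6.2.11.2 and 7.2). That also stands, so a reader should not infer that sites would give same-day doses unthinkingly. These provisions reduce the chance of it without stating the Day 2 rule.

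Three stronger readings are not supported:

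- **That Part B or maintenance dosing is contradictory.** Section 5.2.4 states no same-day rule for note (h) to contradict, so Part B is unclear rather than inconsistent. Figure 3 covers induction only.
- **That Section 6.2.5.4 breaks the same rule** by starting BI-1206 at 100 mg/h from Week 2. Section 5.2.2 withholds faster rates only by implication and names no rate for patients who reacted. Section 6.2.5.4 makes increases depend on the absence of adverse effects and allows the rates to be revised, and the pharmacy guidelines may cover the point.
- **That dose-escalation results are affected.** The DLT definition in Section 3.3 does not depend on the day of rituximab, and it excludes Grade 3 infusion related reactions.

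**Conclusion.** The inconsistency is real but narrow. In Part A, Arm 2, note (h) and the Figure 3 footnote give opposite instructions for a patient who had a significant, non-life-threatening Week 1 reaction, continues both antibodies, and whose infusions fit in one day. It concerns the Week 2, 3 and 4 rituximab doses, three of the four in induction. The arm is estimated at up to 15 patients (Synopsis), a number that could rise if intermediate doses are added (Section 3.6).

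The affected subgroup cannot be sized. The rate of more than 50% in Section 2.2.6 is for rituximab, has no severity split, and cannot be turned into a rate of significant reactions, a term the protocol leaves undefined. The conflict follows from the wording alone. The visit lengths show only that the time test need not replace the reaction test; they rest on assumed BI-1206 rate steps, BSA range and working day. No DLT rule, endpoint or analysis changes. The point merits correction because following note (h) would remove a written precaution.

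**What to change.** Reword the second sentence of note (h) along these lines: *From Week 2, rituximab may follow BI-1206 on the same day only where Week 1 passed without a significant infusion reaction and the infusion times fit; in all other cases rituximab stays on Day 2 (see 5.2.2).*

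State whether the rule also holds in Part B, Arm 2. If it does, add a sentence to Section 5.2.4; if not, limit the reaction condition in note (h) to Part A.

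Two optional clarifications: say who judges a reaction significant and by what standard, since the rewording inherits the undefined term; and add a cross-reference from Section 6.2.5.4 to Sections 5.2.2 and 5.9.2.

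The cost is one or two sentences and no new procedure. Patients who reacted may need a second infusion day in Weeks 2 to 4, which the footnote already requires.

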7.4 Evaluations at 'off-study' visit

The off-study visit will occur when a patient will no longer continue on the treatment portion of the trial (either induction or maintenance treatment). This may be because of any of the reasons outlined in Section 11 or for patients who have completed a year of maintenance therapy. If a patient comes off-study following the Week 8 assessments and prior to commencing maintenance therapy the Week 8 assessments will be considered the "off-study" assessments. At this visit the following investigations where possible will be performed:

- A symptom-directed physical examination including WHO performance status, temperature, pulse rate and seated BP.
- Haematology (see Section 7.1.3).
- Biochemistry (see Section 7.1.3).
- Urinalysis (see Section 7.1.3).
- Serum Immunoglobulins – IgA, IgM & IgG levels will be assessed.
- Beta-2-microglobulin.
- Eye examination as described in Section 7.1.3 within \pm 2 weeks of the off-study visit date.
- ECG: performed if clinically indicated.

- Assessment of disease (unless disease progression has been noted at an earlier assessment or, if the patient has gone on to maintenance therapy and an assessment has been performed within the previous eight weeks (56 days)):

CT scan to assess tumour burden within \pm 2 weeks of the off-study visit date;

- **Patients with lymphomas:** For patients who have FDG PET-avid disease at baseline whose CT scans show a complete response, an FDG-PET scan should be performed within \pm 2 weeks of the off-study visit date.
- **Patients with Waldenström's macroglobulinemia:** a blood sample should be taken for assessment of serum paraprotein.
- Bone marrow aspirate:
 - **CLL Patients:** Those patients who had positive test at baseline and who show a complete response for the first time at a disease assessment at the off-study visit will have a bone marrow sample taken. [REDACTED]
 - **Patients with lymphomas:** Only those patients who had positive test at baseline and who show a complete response for the first time at a disease assessment at the off-study visit will have a bone marrow sample taken. [REDACTED]
- Pharmacodynamic blood sample for assessment of ADA levels, should be taken as described in Section 8.3.
- Assessment of AEs.
- Review of concomitant treatments.

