9.6.3 Eligible patients

For eligible patients, SAE and AE collection and monitoring will commence at the time the patient gives their written consent to participate in the trial by signing the main study consent form and will continue until 125 days after the last administration of BI-1206 and/or rituximab on study (whichever is later) or until the patient starts another anti-cancer therapy.

Should an Investigator become aware of any drug-related SAEs after this 125 day period (even if the patient has started another anti-cancer therapy), these must also be reported to the CDD within the expedited timelines in Section 9.7.

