13.1 Presentation of data

Data will be presented in a descriptive fashion. Variables will be analysed to determine whether the criteria for the trial conduct are met. This will include a description of patients who did not meet all the eligibility criteria, an assessment of protocol deviations, IMP accountability and other data that impact on the general conduct of the trial.

Baseline characteristics will be summarised for all enrolled patients. Patients who died or withdrew before treatment started or did not complete the required safety observations will be described and evaluated separately.

Treatment administration will be described for all cycles. Dose administration, dose modifications or delays and the duration of therapy will be described.

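### All AEs are to be collected to 125 days after the last dose, but the schedule gives Week 8 leavers no AE enquiry after off-study, and note (k) conflicts with 7.5.1 and 9.6.4 on monthly follow-up

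*Combined protocol and SAP*

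**What the plan says.** **Collection window.** Section 7.5.1 states that "SAE and AE monitoring will continue until 125 days after the last administration of BI-1206 and or rituximab on study". Section 9.6.3 sets the same limit for collection and monitoring, or "or until the patient starts another anti-cancer therapy". Neither section limits collection by causality.

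**Monthly follow-up.** Section 7.5.1: "Any drug-related AEs still ongoing after this period will be followed up monthly until resolution to baseline or stabilisation". Section 9.6.4 follows AEs judged at least possibly related until they resolve or stabilise, or new therapy begins. Note (k) to the schedule in 7.6: "Monthly follow-up required ONLY for those AEs and SAEs considered drug-related (highly probable, probable or possible) and present at off-study". Note (k) does not mention the 125 days.

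**Visits.** Section 7.4 makes Week 8 the off-study visit in this case: "If a patient comes off-study following the Week 8 assessments and prior to commencing maintenance therapy". The schedule puts Week 8 at Day 50, with up to one week's allowance. AEs are assessed at off-study. After that, section 7.5.2 says: "Survival (and if applicable, disease status) will be captured every approximately every 16 weeks from the off study visit", continuing to one year from first treatment and six-monthly afterwards. It does not name AEs at these contacts.

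**Use of the data.** Documenting AEs and SAEs is a primary endpoint in Parts A and B (3.1.1). Section 13.1: "Data will be presented in a descriptive fashion". Section 13.2 gives a start for safety data (consent) but no end date for the AE tables.

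**The concern.** The protocol sets a 125-day obligation, and the schedule that sites work from contains no visit or call that would meet it. The only instruction in the schedule on AEs after off-study is note (k), which follows a different rule from 7.5.1.

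This is a first-in-human trial with AE documentation as a primary endpoint. Section 5.9.8 accepts that long-term effects are not known, and section 2.2.8 lists infection and autoimmune disease among the possible toxicities. Patients on maintenance are asked about AEs before each eight-weekly dose (7.3). Patients who leave at Week 8 have no scheduled enquiry after that visit unless they left with a related event. If fewer late events are recorded in the second group, the descriptive AE tables mix two levels of ascertainment, and a reader cannot tell a lower event rate from fewer questions.

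**Working it through.** The check is calendar arithmetic plus a comparison of the follow-up rules. No sample size, power or alpha bears on it.

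**1. Reproduce the plan's own figure.** Weekly doses fall on Days 1, 8, 15 and 22. Section 10.3.1 places Week 8 four weeks after the last induction dose: 22 + 28 = Day 50, which matches the schedule.

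**2. Patient who leaves at Week 8.**
- Window end = last dose + 125 = 22 + 125 = Day 147.
- First later contact = off-study + 16 weeks = 50 + 112 = Day 162, which is 162 − 22 = 140 days after the last dose and 162 − 147 = 15 days after the window closes.
- Days with no scheduled contact = 147 − 50 = 97 of 125 (78%).

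**3. Sensitivity.**
- Off-study on Day 57 (latest allowed): contact on Day 169; gap 147 − 57 = 90 days (72%).
- Approximately 16 weeks read as up to two weeks early (my assumption): 50 + 98 = Day 148, still one day outside.
- Last rituximab dose on Day 23: window to Day 148, gap 98 days. Only this case combined with the early contact just reaches the window end, and that contact still does not name AEs.

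**4. When a 16-week contact does fall inside.** With d days from last dose to off-study, d + 112 ≤ 125 requires d ≤ 13.

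**5. Maintenance patients.** Doses every 56 days from Day 57–70 up to Day 365 give six doses. At 6 mL each this is 36 mL, which agrees with the maintenance PK volume in 8.3.1. The documents do not give d for these patients; values from 0 to 70 days were tried, with the one-year contact taken as Day 365.

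| Last dose | Window ends | Later contact inside the window? |
|---|---|---|
| Maintenance 1 to 4 | dose + 125 | Yes if d ≤ 13; no at d = 28, 56, 70 |
| Maintenance 5 (Day 281–294) | Day 406–419 | Yes, Day 365, at every d tried |
| Maintenance 6 (Day 337–350) | Day 462–475 | Yes, Day 365, if off-study comes before it; otherwise no |

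**6. The follow-up rules side by side.**

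| Related AE | 7.5.1 | 9.6.4 | Note (k) |
|---|---|---|---|
| Starts Day 80, still ongoing after Day 147 | Monthly follow-up | Followed | Not followed: absent at off-study |
| Present at Day 50 | Monthly only if still ongoing after the window | Followed | Monthly, by implication from off-study |

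Note (k) and 7.5.1 differ both on which events qualify and on when monthly follow-up starts.

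**The case against.** The strongest reply is that note (k) governs how often known events are chased, not whether new ones are collected. That is right. A reader might infer that note (k) ends AE collection at off-study, but its text does not say so. Sections 7.5.1 and 9.6.3 still bind sites to day 125, 9.8 requires all AEs of eligible patients in the eCRF, and limiting follow-up to related events agrees with 9.6.4. What remains is the conflict over which related events are followed and from when.

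The off-study visit also lies inside the window and assesses AEs. The gap is therefore one of scheduled enquiry after off-study, and step 5 shows that some patients do have a later contact in time.

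The 97 days are reduced when new therapy starts. Patients leaving at Week 8 will often lack stable disease, so some windows will close early; the documents do not say how many.

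A contact on Day 162 could still pick up events with onset by Day 147, by recall. So the 15 days matter less than the fact that the contact does not ask about AEs. The schedule's survival column also mentions clinic visits, where events could surface, but it sets no AE enquiry there.

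Serious events are better protected. SAEs are due within 24 hours of the site learning of them, related SAEs stay reportable after the window, and section 11 asks for every effort to complete safety follow-up. These routes depend on the site becoming aware; they do not schedule a question.

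**Conclusion.** The point holds as an unimplemented collection window and a conflict between follow-up rules. For a patient who leaves at Week 8 without an ongoing related AE, 97 of 125 days (90 if off-study is on Day 57) have no scheduled AE enquiry. This assumes a last dose on Day 22, a contact interval of 112 days and no new therapy before Day 147. New events, mainly non-serious or unsolicited, may be under-recorded relative to patients asked every eight weeks on maintenance.

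Three stronger readings are tempting and not supported:
- That most patients are affected. The documents give no share leaving at Week 8 and no rate of new therapy, so the share could be anywhere from 0 to 1.
- That late toxicity is missed. The collection duty still stands, so it may be missed.
- That the RP2D will look safer than it is. DLTs close at Week 5, before the gap opens, so DLT counts are unaffected. Sections 3.3 and 3.4 let cumulative and other toxicity inform the RP2D, so an effect is possible, but none is shown.

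**What to change.** 1. Reword note (k) to agree with 7.5.1, 9.6.3 and 9.6.4: all AEs and SAEs collected to 125 days after the last dose or the start of new anti-cancer therapy, and related AEs that start after off-study followed as well as those present then. State one starting point for monthly follow-up.
2. In 7.5.2 and 7.6, add an AE/SAE and new-therapy enquiry at the first contact after off-study, covering events with onset up to day 125 after the last dose. Time it at or near day 125 where this does not displace the one-year survival contact.
3. Treat late-maintenance patients separately. With a last dose on Day 281–294, day 125 is Day 406–419, past the one-year contact on Day 365. That contact should stay, and the protocol should say how the remaining days are covered, for example by the same question at the next contact.
4. State the same AE cut-off in 13.2, so that the tables cover a defined period.

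Cost: protocol wording, one AE page at an existing contact, and more late AEs recorded. The first contact moves about 15 days earlier for a Week 8 leaver (Day 162 to about Day 147) and up to 13 days later for a patient whose off-study visit was within 13 days of the last dose.
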